- **Interventions:** Participants will be randomized in a 1:1:1:1 ratio in permuted blocks of 4-12 to one of four interventions as summarized in **Table 1** and described in detail below. Randomization will be generated through sealedenvelope.com and allocation through REDCap. Randomization will be stratified by race.

Table 1: Summary of blood pressure (BP) interventions and factorial design

		Postpartum BP Goals	
Interventions		(C) Standard control BP <150/100	(D) Tight control BP <140/90
BP monitoring	(A) OB Provider Monitoring	(#1) Standard control Provider Monitoring	(#2) Tight control Provider Monitoring
	(B) Augmented Remote Monitoring	(#3) Standard control Remote monitoring	(#4) Tight control Remote monitoring

Blood Pressure Care Navigation

(A) *Obstetric Provider Monitoring (In-Person)*: Participants will be instructed to check their blood pressures twice a day for two weeks and daily for weeks 3-6 after delivery and report abnormal blood pressures or symptoms to their obstetric clinicians. Additional postpartum visits beyond the blood pressure check will be directed by their obstetric clinician.

(B) *Augmented Remote Blood Pressure Monitoring*: A physician investigator (fellow or attending) will place an order for "MyHealth BP Flowsheet" in the participant's chart, which triggers the Track My Health feature on MyHealth. The research assistant will demonstrate to the participant how to track blood pressures through the Track My Health feature on the MyHealth smartphone app. Blood pressure monitoring and management plan outlined below. Among women on antihypertensive medication, blood pressure tracking, monitoring, and feedback will continue until care has been transferred to a clinician who can provide long-term care.

Participant and Hypertension Program Manager responsibilities described in detail below:

Table 2. Participant and Hypertension Program Manager Responsibilities

Blood Pressure Monitoring	Participants Responsibilities	Hypertension Program Manager Responsibilities
Weeks 1-2 after delivery	
 ▶ Check blood pressures twice daily ▶ Record BPs every day in MyHealth ▶ Seek urgent care (triage, ED) for sustained severe HTN or symptoms 	
 ▶ Receive BPs notifications daily M-F ▶ Call patients who do not send BPs ▶ Adjust antihypertensive medications based on sections (C) and (D) below

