- ▶ **Survey 3**: (12-weeks after delivery): Participants will be contacted via SMS text or email to ask about follow up with a primary care physician and chronic hypertension. Participants will receive a \$20 gift card for completion of this survey.

OUTCOMES

Primary Outcomes: The outcome for the R21 and listed on ClinicalTrials.gov is the proportion of patients with a blood pressure recorded in the office at 7-10 days postpartum (**BPinperson**). It is not hypothesized that the primary outcome varies by the blood pressure control intervention but will vary by the blood pressure management intervention.

Secondary Outcomes: We will examine three categories of secondary outcomes (**Table 3**). *Hypertension control and adverse events* includes measures of blood pressure control and events potentially associated with poor blood pressure control such as severe maternal morbidity (SMM) and hospital readmission. Given that our intervention tests different models of care, we will assess *health care utilization* associated with these models including adherence to in-person and remote blood pressure monitoring, medication use, attendance at scheduled visits, and unscheduled visits to an urgent care or emergency room.

We will also examine a variety of *patient-reported outcome measures* especially satisfaction with care. HDP carries not only a risk of long-term health sequelae, but also post-traumatic stress disorder, depression, and anxiety.^{92,93} In a review of patients' experiences with HDP, the potential for worsening or chronic hypertension was associated increased feelings of anxiety and loss of agency.⁹⁴ We hypothesize that augmented remote monitoring and tighter blood pressure control, both individually and in combination, will improve postpartum blood pressure control within the first six weeks postpartum. We also hypothesize that participants, especially Black participants, will find the results of these interventions satisfying and acceptable as they provide a nexus of agency during otherwise stressful life events. Observed reductions in blood pressure provide more frequent and immediate feedback to participants relative to other meaningful outcomes such as SMM or hospital readmission. We also acknowledge the possibility that patients also could find frequent observation of blood pressures and tighter parameters to be burdensome or increase anxiety about health status.

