While postpartum patient-reported outcome measures have been developed and validated to study inpatient recovery, lack of consensus exists regarding optimal measures of outpatient recovery.⁹⁵ In a recent systematic review of validated measures used to assess three domains or more of outpatient postpartum recovery, three measures were identified but all had significant limitations.⁹⁶ The authors conclude that assessment may be better achieved using existing methods such as those endorsed by the Patient-Reported Outcomes Measurement Information System initiative (PROMIS).⁹⁶ Therefore, we selected validated PROMIS and NIH Toolbox measures related to depression, anxiety, and social support. Because experience of being listened to or being ignored and dismissed are central drivers of Black women's pregnancy and postpartum experience and health outcomes,^{38,39} we emphasize outcomes related to communication during and satisfaction with clinical encounters such as the Communication Assessment Tool -Team (CAT-T) and the Mothers on Respect

index (MORI), a scale developed to assess the nature of respectful patient-provider interactions and their impact on a person's sense of comfort, behavior, and perceptions of racism or discrimination.

ENROLLMENT AND FEASIBILITY

During 2021, 22% (n=1120) of patients delivering at VUMC had a diagnosis of HDP, most commonly gestational hypertension, preeclampsia, and chronic hypertension and 22% of these patients were Black. We have used the eligibility, enrollment, and follow up estimates in **Table 5**. With an aim for 50% of our participants to self-identify as Black, we estimate that we can enroll a total sample size of 1000 patients with 6-week follow data after 4-years. Enrollment and follow up estimates are based on prior observational and intervention studies performed among postpartum patients.¹⁰⁰⁻¹⁰²

Table 5 : Estimated Enrollment Numbers

	Black patients annually	Black patients 4 years	Total sample size 4 years
Total deliveries with HDP	246	986	1971
Eligible for study (95%)	234	936	1873
Agree to enroll (75%)	176	702	1404
Retained to 6 weeks (75%)	132	527	1053

ANALYTIC APPROACH

Specific Aim 1: To assess whether augmented remote blood pressure monitoring and tight blood pressure control, both individually and in combination, improve blood pressure control and the frequency of severe hypertension in the first 2 weeks postpartum.

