Aim 1 Analytic Approach: Our primary analysis will examine the independent effect of the interventions (blood pressure goals and monitoring approach) on the primary outcomes. While randomized trials greatly reduce confounding, they do not eliminate it, and covariate adjustment enhances statistical power. Balance in participant's demographic and clinical characteristics across the four groups (control + 3 interventions) will be compared using the Mann-Whitney *U* test for continuous variables and Chi squared test for categorical variables. Characteristics that exhibit differences across groups and potential confounding variables such as race, socioeconomic status, and medical comorbidities will be considered as adjusting covariates in the subsequent regression analysis. Multiple linear regression with ordinary least square estimates (OLS) will be used to compare the SBP and DBP primary outcomes across four interventions with a binary variable for the monitoring intervention (standard vs augmented), a binary variable for the blood pressure goal intervention (standard 150/100 and tight 140/90) and an interaction term between the two binary variables for the combined interventions. A negative value for two main effects of interventions indicates better blood pressure control using individual interventions alone than the standard of care. A negative value for the interaction effect indicates better blood pressure control using combined intervention than individual intervention alone. Post hoc analysis of variance (ANOVA) can be conducted to assess the overall effect of each individual interventions (with 2 degree of freedom) and the overall intervention effects (with 3 degree of freedom). Although OLS does not require normality assumption for outcomes and residuals, extreme outliers might result in potential bias. In this case, a non-parametric model (e.g. proportional odds model) will be considered. This analysis will be repeated allowing the primary outcome to include mean blood pressures reported via augmented remote monitoring among women who do not attend in-office visits. Multiple logistic regression will be conducted for binary outcomes including the severe hypertension primary outcome, hypertension secondary outcomes and healthcare utilization secondary outcomes. The same main effects and interaction effects for interventions specified for the linear regression model will be included with negative values for the log-odds ratio indicating improved outcomes in the intervention groups. Linear regression with OLS will be used for patient-reported secondary outcome measures in a similar fashion as SBP and DBP primary outcomes. Given the prospective design and dedicated personnel, we anticipate little missing covariate data. In case there are more than 1% participants with missing data in the analysis, multiple imputation will be conducted as sensitivity analysis. All outcomes will be analyzed as intent-to-treat.

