
Specific Aim 2: To test whether these interventions narrow the existing Black/non-Black inequity in postpartum outcomes such as blood pressure control and severe hypertension.

Aim 2 Analytic Approach: Given racial disparities in postpartum outcomes and hypothesized heterogeneity of intervention effect, we plan for two pre-specified subgroup analysis in (1) standard care only (N=250) (2) Black participants only (N=500). The first subgroup analysis aims to assess racial disparities in postpartum outcomes without intervention where Black/non-Black will be the main effect of interests. The second subgroup analysis aims to reassess intervention effects observed in Aim 1 but within Black participants. To test the hypothesis of the interventions narrowing racial inequity,

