we will use the overall cohort (N=1000) and additionally include the interaction between Black/Non-Black and the intervention effects (two main effects + one interaction effects) on top of all models in Aim 1. Missing data will be handled in the similar fashion as Aim 1. **Power and Sample Size Considerations (All Aims):** For Aim 1, power consideration is conducted in the setting of two group comparisons with sample size of N=250 (N=75 for Aim 3) in the standard care group and N=500 (N=150 for Aim 3) for each individual intervention instead of in the setting of 2x2 factorial design with N=1000 (N=300 for Aim 3) because the effect size of F-statistics for continuous outcomes and chi-square statistics for binary outcomes is not clinically interpretable. Review of institutional data found that 10.2% of patients with HDP at delivery experience sustained severe hypertension within the first 6 weeks postpartum and these patients have a mean SBP of 138 (SD 17.2) and mean DBP of 83 (SD 11.9). We will have 80% power to detect a minimum of 0.22 standardized reduction in SBP and DBP (a small effect by Cohen's nomenclature¹⁰³) which corresponds to reduction in SBP from 138 to 134 mmHg and DBP from 83 to 80 mmHg. Additionally, we will have 80% power to detect 57% reduction in sustained severe hypertension. Minimum detectable effect sizes for selected secondary outcomes in Aim 1 and the primary outcome for Aim 3 are provided (Table 6). For Aim 3, we will have 80% power to detect a minimum of 0.4 standardized difference in cardiovascular outcomes (a medium effect by Cohen's nomenclature), which corresponds to an increase of lateral e' from 11.7 to 13.1. For Aim 2, power justification is conducted based on N=300 using analysis of variance (ANOVA) for the interaction terms between race and interventions effects (with 3 degree of freedom) for the SBP and DBP primary outcomes. The minimum detectable F-statistics for the overall interaction term is 0.19 which is small-to-medium effect by Cohen's nomenclature. The power consideration does not consider adjusting covariates and thus is conservative since inclusion of adjusting covariates will improve the power of the study.

Table 6: Minimum detectable Relative Risk (alpha=0.05, 80% power, N=1000)

Outcome	Baseline	Minimum Detectable RR or Effect Size
Mean systolic blood pressure (SD)	138 (17.2)	4
Mean diastolic blood pressure (SD)	83 (11.9)	3
Sustained severe blood pressure (%)	10%	43%
Postpartum visit attendance (%)	40%	63%

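### The logistic models have no rule for rare events, so the race-by-intervention result for severe maternal morbidity would probably have no finite three-way estimate if its rate is below about 2%

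*Combined protocol and SAP*

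**What the plan says.** Under OUTCOMES, one category of secondary outcome covers blood pressure control and "events potentially associated with poor blood pressure control such as severe maternal morbidity (SMM) and hospital readmission". Table 3 lists SMM (6 weeks) and readmission for hypertension (3 weeks) under Hypertension Outcomes.

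The Aim 1 Analytic Approach assigns the severe hypertension primary outcome, the hypertension secondary outcomes and the utilization secondary outcomes to multiple logistic regression: "The same main effects and interaction effects for interventions specified for the linear regression model will be included". Adjusting covariates may be added. A negative log-odds ratio is to be read as benefit.

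The Aim 2 Analytic Approach adds race by both main effects and by their product "on top of all models in Aim 1". It also plans two subgroup analyses: "standard care only (N=250) (2) Black participants only (N=500"). The second repeats the Aim 1 models in Black participants.

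Only two fallbacks are given: a proportional odds model if a continuous outcome has extreme outliers, and multiple imputation for missing data. No penalised, exact or reduced model is named, and no minimum event count. Table 6 ("alpha=0.05, 80% power, N=1000") gives baseline rates for severe hypertension and for visit attendance, but none for SMM or readmission.

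**The concern.** With two binary factors and their product, the Aim 1 model has as many intervention parameters as arms. Adding race and its three products gives eight parameters for eight race-by-arm cells. Such a saturated model reproduces the observed log-odds in each cell, and these are minus infinity in a cell with no event. Software then stops at an arbitrary iteration and prints a very large coefficient with a meaningless Wald standard error. The sign of the coefficient depends on which cell happened to be empty, yet the plan reads the sign as benefit or harm.

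The protocol describes its target population as being at risk of severe morbidity and says all outcomes will be stratified by race, so readers will look for SMM by race. Without a stated rule, the analyst would either report such a number or choose a remedy after seeing the data.

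**Working it through.** **Inputs**
- Allocation: "Participants will be randomized in a 1:1:1:1 ratio" (STUDY PROCEDURES, Interventions), so 1000/4 = 250 per arm.
- Race mix: "With an aim for 50% of our participants to self-identify as Black" (ENROLLMENT AND FEASIBILITY), so 250/2 = 125 per race-by-arm cell.
- Enrolled: 1,404 (Table 5), so 1404/8 = 175 or 176 per cell if all are analysed.
- Event rate p for SMM: not in the documents. Assumed 0.5% to 5%, equal in all cells unless stated.

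**Step 1: the nearest stated figure.** None exists for SMM or readmission. The closest is 80% power for a 57% reduction in sustained severe hypertension from 10.2%, with "sample size of N=250 (N=75 for Aim 3) in the standard care group and N=500 (N=150 for Aim 3) for each individual intervention". Here p1 = 0.102, p2 = 0.43 × 0.102 = 0.0439, allocation ratio r = 2 and two-sided alpha is 0.05 (sidedness assumed).

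n = [1.96·√((1+1/r)·p̄·q̄) + 0.8416·√(p1·q1 + p2·q2/r)]² / (p1−p2)², with p̄ = (0.102 + 2 × 0.0439)/3 = 0.0632.

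This gives n = 223 in the standard-care group, or 248 with continuity correction, against 250 stated. The figure reproduces, so the group sizes are being read as the plan intends.

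**Step 2: what one empty cell does.** The three-way coefficient is a sum of the eight cell log-odds with signs +1 and −1. If any cell has no events, that sum is not finite. The Aim 1 product behaves the same way over four cells. Adjusting covariates do not rescue it, because the model's terms can still isolate the empty cell.

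**Step 3: how often this happens.** P(at least one empty cell) = 1 − [1 − (1−p)^n]^k for k cells of n women.

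Example, Aim 2 at 1%: 0.99^125 = 0.2847; 1 − 0.2847 = 0.7153; 0.7153^8 = 0.0685; result 93%.

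Example, Aim 1 at 1%: 0.99^250 = 0.0811; 0.9189^4 = 0.7131; result 29%.

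| Assumed rate | Events per cell of 125 | Aim 2, 8 × 125 | Aim 2, all 1,404 | Black-only refit, 4 × 125 | Aim 1, 4 × 250 |
|---|---|---|---|---|---|
| 0.5% | 0.625 | 99.8% | 99% | 95% | 74% |
| 1% | 1.25 | 93% | 78% | 74% | 29% |
| 2% | 2.5 | 49% | 21% | 28% | 2.5% |
| 3% | 3.75 | 16% | 4% | 9% | 0.2% |
| 5% | 6.25 | 1.3% | 0.1% | 0.7% | below 0.1% |

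The Aim 2 probability passes 50% at a rate of 1.97% with N=1000 (19.7 events) and at 1.41% with 1,404 (0.0141 × 1404 = 19.8 events). Either way the even-odds point is about 20 events in total. For Aim 1 it is about 0.73%.

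**Step 4: departures from the base case (Aim 2, N=1000)**
- 22% Black, the 2021 source mix in ENROLLMENT AND FEASIBILITY, instead of 50%: cells of 55 and 195; 81% at 2% and 57% at 3%. The even-odds point moves to 3.3%, about 33 events.
- Relative risk 0.43 (the plan's detectable effect for severe hypertension) in all three intervention arms: 93% at a 2% control rate, 74% at 3%, 52% at 4%.
- Dropping only the three-way term, by simulation: some coefficient is still non-finite in about 54% of trials at 1% and 8% at 2%.
- Sustained severe hypertension at 10.2%: about 0 under equal rates, and about 2% with relative risk 0.43 in all three intervention arms. It reaches 19% only if both reductions multiply in the combined arm (0.43² × 10.2% = 1.9%).

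**The case against.** Several points on the other side stand.

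- **The rate is assumed.** A reader might infer that the Aim 2 model will usually break down whatever the rate. The documents do not support that, because they give no SMM rate. Under equal rates, breakdown is the likelier outcome only below about 2%, or about 1.4% if all 1,404 are analysed. The larger number is relevant because analysis is by intention to treat and health records are reviewed.
- **Readmission.** It sits beside SMM in the plan's wording, so a reader might take it as equally affected. Nothing shows it to be that rare; at 5% the figure is 1.3%.
- **Aim 1.** A reader might extend the problem to the Aim 1 product. At 1% the figure is 29% and at 2% it is 2.5%, so that model is mostly estimable from about 1% upward.
- **Not everything is lost.** An empty cell always removes the three-way coefficient. Some lower-order coefficients can stay finite, and a likelihood-ratio test can still be computed. The Aim 2 power statement is itself framed as an overall 3-degree-of-freedom test, though for SBP and DBP only.
- **Method not named.** The plan says multiple logistic regression, not maximum likelihood or Wald tests. Those are the ordinary readings, and a penalised fit would not contradict the text.
- **Importance.** SMM is a secondary outcome with no power claim, and both aims name blood pressure control and severe hypertension.

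These points narrow the concern. They do not supply the missing rule: as written, the model applies to SMM, and at a low rate its race-by-intervention result is not usable.

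**Conclusion.** The concern holds in a conditional form. The plan applies one saturated logistic specification to all binary hypertension and utilization secondary outcomes and makes no provision for sparse events. At an SMM rate of 1% or less (10 or fewer expected events in 1000) the Aim 2 three-way coefficient is non-finite in at least 93% of trials with N=1000, and at 2% in about half. The Black-only refit is also exposed.

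These figures rest on an assumed rate, equal rates across cells, a 50% Black sample and the ordinary maximum-likelihood reading. Effective interventions or a lower Black share would raise them; analysing all 1,404 would lower them.

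The SBP and DBP primary analyses are linear models and do not have this problem, and sustained severe hypertension is common enough to be essentially unaffected. This is worth correcting before the data are analysed, but it does not threaten the primary conclusions.

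**What to change.** Add a sparse-event rule to the analytic approach:

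1. State the expected SMM and readmission rates, with their source.
2. Apply the rule to SMM, and to any other binary secondary outcome whose event count, pooled over arms and read blind to allocation, makes empty race-by-arm cells likely. About 20 or fewer events in 1000 is a workable trigger at 50% Black; reset it from the achieved cell sizes if the race mix differs.
3. For these outcomes, replace ordinary logistic regression with Firth-penalised logistic regression and profile-likelihood intervals.
4. Report event counts by arm and by race within arm, and a risk difference for each factor with a score interval.
5. Label any product-term estimates for these outcomes as descriptive only.
6. Keep ordinary logistic regression for common outcomes such as sustained severe hypertension.

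There is no need to forbid product terms: the penalised fit gives finite estimates, and Aim 1 asks about the interventions in combination. The cost is a few sentences of SAP text, a standard software option and a little more analysis work. The downside is that interaction results for rare outcomes are descriptive, and at these event counts the data could not support more.

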Weeks 3-6 after delivery	
 ▶ Check blood pressures once daily ▶ Record BPs daily in MyHealth ▶ Seek urgent care (triage, ED) for sustained severe HTN or symptoms 	
 ▶ Receive BPs notifications weekly ▶ Adjust antihypertensive medications based on sections (C) and (D) below
Communication with obstetric clinicians		
 ▶ Send updates on HTN management at weeks 2, 4, and 6 ▶ Document medication changes in EStar ▶ Send updates to non-VUMC obstetric clinicians with any antihypertensive medication changes
Care Handoffs	
 ▶ Schedule postpartum visit at 4-6 weeks ▶ Schedule a visit with a primary care clinician or cardiologist at month 3 	
 ▶ Ensure that postpartum visits are scheduled by 4-6 weeks ▶ Ensure that primary care or cardiology visits are scheduled at month 3 ▶ Remind patients about all visits

Blood pressure Control

(C) *Standard Blood Pressure Control*: Blood pressure targets will be <150 mmHg systolic and <100 mmHg diastolic consistent with current postpartum recommendations from ACOG. Blood pressure notifications for the HTN program navigator will reflect these parameters and medications will be initiated or titrated to meet these goals. See Appendix J for specifics on management and Appendix L for recommended medication regimens

(D) *Tight Blood Pressure Control*: Blood pressure targets will be <140 mmHg systolic and <90 mmHg diastolic. Blood pressure notifications for the HTN program navigator will reflect these parameters and medications will be initiated or titrated to meet these goals. See Appendix K for specifics on management and Appendix L for recommended medication regimens.

- ▶ **Survey 2** (6-weeks after delivery): Participants will receive the survey via text web-link or email link. Survey 2 asks questions about the participant's experience managing hypertension after delivery, the Mothers On Respect Index (MORI) and the Communication Assessment Tool geared towards postpartum care, the PROMIS Bank v1.0 Anxiety (adaptive) survey, the PROMIS Bank v1.0 Depression (adaptive) survey, the PROMIS Bank v2.0 Instrumental Support (adaptive) survey. We estimate that this survey will take 20 minutes to complete. Participants will receive a \$20 gift card for completion of this survey.

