While postpartum patient-reported outcome measures have been developed and validated to study inpatient recovery, lack of consensus exists regarding optimal measures of outpatient recovery.⁹⁵ In a recent systematic review of validated measures used to assess three domains or more of outpatient postpartum recovery, three measures were identified but all had significant limitations.⁹⁶ The authors conclude that assessment may be better achieved using existing methods such as those endorsed by the Patient-Reported Outcomes Measurement Information System initiative (PROMIS).⁹⁶ Therefore, we selected validated PROMIS and NIH Toolbox measures related to depression, anxiety, and social support. Because experience of being listened to or being ignored and dismissed are central drivers of Black women's pregnancy and postpartum experience and health outcomes,^{38,39} we emphasize outcomes related to communication during and satisfaction with clinical encounters such as the Communication Assessment Tool -Team (CAT-T) and the Mothers on Respect index (MORi), a scale developed to assess the nature of respectful patient-provider interactions and their impact on a person's sense of comfort, behavior, and perceptions of racism or discrimination.

VARIABLE NAME	DESCRIPTION	DERIVATION	VALUE
7-10 Day Outcomes			
BPinperson710	BP recorded in person	None	1=yes 0=no
BPMremote710	Any BP recorded remotely	A systolic BP (d710sbp_remote) or a diastolic BP (d710dbp_remote) value is present	1=yes 0=no
BPanyp710	Any BP recorded in person or remotely	If BPinperson710 = 1 or BPMremote710=1	1=yes 0=no
SBP710	SBP value Selected by the following hierarchy: 1) in person SBP, 2) remote SBP - If multiple remote BP values were submitted, selected the SBP from day 8 and average the values.	SBP710 = d710sbp_inperson if d710sbp_inperson is present. If d710sbp_inperson is absent, then use d710sbp_remote.	Continuous
DBP710	DBP value Selected by the following hierarchy: 1) in person DBP, 2) remote DBP - If multiple remote BP	DBP710 = d710dbp_inperson if d710dbp_inperson is present. If	Continuous

	values were submitted, selected the DBP from day 8 and average the values.	d710dbp_inperson is absent, then use d710dbp_remote.	
SBP710_bin	SBP value \geq 140	SBP710 \geq 140	1=yes 0=no
DBP710_bin	DBP value \geq 90	DBP710 \geq 90	1=yes 0=no
ANYhigh_bin	Any BP value \geq 140/90	SBP710 \geq 140 OR DBP710 \geq 90	1=yes 0=no
SBPsevere710_bin	SBP value \geq 160	SBP710 \geq 160	1=yes 0=no

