DBPsevere710_bin	DBP value \geq 110	DBP710 \geq 110	1=yes 0=no
ANYsevere_bin	Any BP value \geq 160/110	SBP710 \geq 160 OR DBP710 \geq 90	1=yes 0=no
dcp_medstart	Any medication started between discharge through week 6 after delivery	n/a	1=yes 0=no
dcpp_medstart	Days postpartum that medication was started	n/a	Continuous
readmit	Hospital readmission	n/a	1=yes 0=no

The two co-primary outcomes are mean systolic blood pressure (SBP) and diastolic blood pressure (DBP) recorded in-office (**Table 3**). In a secondary analysis, we will also include mean blood pressure measurements reported via augmented remote monitoring among women who do not attend in-office visits. The third co-

primary outcome is proportion of participants with sustained severe hypertension during the first 6 weeks postpartum defined as a SBP ≥ 160 or a DBP ≥ 110 on two occasions at least 15 minutes apart.

Secondary Outcomes

We will examine three categories of secondary outcomes (**Table 3**). *Hypertension control and adverse events* includes measures of blood pressure control and events potentially associated with poor blood pressure control such as severe maternal morbidity (SMM) and hospital readmission. Given that our intervention tests different models of care, we will assess *health care utilization* associated with these models including adherence to in-person and remote blood pressure monitoring, medication use, attendance at scheduled visits, and unscheduled visits to an urgent care or emergency room.

Table 3: Study outcomes and time frame for assessment

Hypertension Outcomes		
Blood pressure control (Primary Outcome)	Mean SBP assessed in-office and through all methods	7-10 days
Blood pressure control (Primary Outcome)	Mean DBP assessed in-office and through all methods	7-10 days
Severe hypertension (Primary Outcome)	SBP ≥ 160 or DBP ≥ 110 on two occasions 15 minutes apart and less than 4 hours apart	6 weeks
Hospital readmission	Readmission for hypertension management after delivery discharge	3 weeks
Severe maternal morbidity	Center for Disease Control criteria	6 weeks
Health Care Utilization		
Blood pressure assessment	Proportion who report at least one BP reading post delivery	7-10 days
Medication use	Proportion requiring and/or initiating antihypertensive medications	6 weeks
Urgent care visit	Visit to obstetric triage or an emergency department for hypertension	3 weeks

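### ANYsevere_bin is derived with a diastolic cut-off of 90 instead of 110, so about three times too many women would be coded severe at days 7-10

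*Combined protocol and SAP*

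**What the plan says.** The OUTCOMES section contains a table of derived variables headed as day 7-10 outcomes. Its rows bear on each other as follows.

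- **ANYsevere_bin**, description: "Any BP value \geq 160/110".
- **ANYsevere_bin**, derivation: "SBP710 \geq 160 OR DBP710 \geq 90".
- **DBPsevere710_bin**, the row above: "DBP value \geq 110", with the same cut-off in its derivation. SBPsevere710_bin uses 160 in both columns.
- **ANYhigh_bin**, the composite for ordinary high blood pressure: "SBP710 \geq 140 OR DBP710 \geq 90".

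In the text after the table, the third co-primary outcome is sustained severe hypertension, "defined as a SBP ≥ 160 or a DBP ≥ 110 on two occasions at least 15 minutes apart". Table 3 uses the same two thresholds. So do the discharge information under STUDY PROCEDURES and the participant messages in Appendices B to E.

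For the tight-control arm, section (D) of the interventions states: "Blood pressure targets will be <140 mmHg systolic and <90 mmHg diastolic". Section (C) sets the standard-arm diastolic target at below 100.

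**The concern.** The description and the derivation in one row give different diastolic cut-offs, and no reading reconciles them. The 90 matches DBP710_bin and ANYhigh_bin, which suggests it was carried down from the ANYhigh_bin row.

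If the derivation is coded literally, two things follow. First, every woman with DBP710_bin = 1 is also coded severe, including women who are 0 on both severe components. Second, the wrong cut-off is exactly the tight-arm diastolic goal, while the standard arm aims for below 100. The variable would then largely record whether the tight diastolic goal was met. A modest fall in diastolic pressure could look like a substantial fall in severe hypertension. Aim 1 asks about the frequency of severe hypertension in the first two weeks, and Aim 2 carries severe hypertension into the Black/non-Black comparison, so a wrong day 7-10 variable could mislead on both.

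**Working it through.** **Inputs from the plan.** The power section gives "mean SBP of 138 (SD 17.2) and mean DBP of 83 (SD 11.9"), and Table 6 uses the same values as general baselines. The cut-offs are those listed above. The plan gives no correlation between systolic and diastolic pressure and no expected rate for ANYsevere_bin. I assume bivariate normality and vary the correlation r from 0 to 0.9.

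**Reproducing the plan's own figure.** The plan claims 80% power for a 0.22 SD reduction with 250 against 500 (two-sided alpha 0.05 assumed, since sidedness is not stated).

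- Standard error in SD units: √(1/250 + 1/500) = 0.0775.
- Detectable difference at 80% power: (1.960 + 0.842) × 0.0775 = 0.217 SD.
- In mmHg: 0.217 × 17.2 = 3.7 systolic and 0.217 × 11.9 = 2.6 diastolic, printed as 4 and 3.
- Power at 0.22 SD: Φ(0.22/0.0775 − 1.960) = 0.811.

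The plan's figure is reproduced.

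**Single cut-offs at baseline means.**

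- P(SBP ≥ 160) = 1 − Φ((160 − 138)/17.2) = 1 − Φ(1.279) = 10.0%.
- P(DBP ≥ 110) = 1 − Φ((110 − 83)/11.9) = 1 − Φ(2.269) = 1.2%.
- P(DBP ≥ 90) = 1 − Φ((90 − 83)/11.9) = 1 − Φ(0.588) = 27.8%.

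**The composite.** P(flag) = 1 − P(SBP < 160 and DBP < cut). At r = 0.6 this is 1 − 0.895 = 10.5% with the cut at 110, and 1 − 0.693 = 30.7% with the cut at 90.

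| r | As described (110) | As printed (90) | Ratio | Flagged women who are not severe | Flagged women with DBP ≥ 90 |
|---|---|---|---|---|---|
| 0 | 11.1% | 35.1% | 3.16 | 68% | 79% |
| 0.5 | 10.6% | 31.6% | 2.98 | 66% | 88% |
| 0.6 | 10.5% | 30.7% | 2.94 | 66% | 91% |
| 0.7 | 10.3% | 29.9% | 2.90 | 65% | 93% |
| 0.9 | 10.1% | 28.1% | 2.80 | 64% | 99% |

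The fifth column is (printed − described)/printed: the women with diastolic pressure from 90 to below 110 and systolic pressure below 160. The last is P(DBP ≥ 90) divided by the printed-rule rate.

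**Sensitivity.** At the plan's target means of 134/80 the rates are 6.5% to 7.1% as described and 20.3% to 25.3% as printed, a ratio of 3.1 to 3.6. A half-unit continuity shift for whole-mmHg readings moves the ratio by no more than 0.03.

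**Effect on an arm comparison (illustration).** Let mean diastolic pressure fall from 83 to 80, the plan's detectable difference, with systolic pressure unchanged and r = 0.6. The described rule goes from 10.5% to 10.2%. The printed rule goes from 30.7% to 24.1%, an apparent drop of 6.6 percentage points against a real one of about 0.3.

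**The case against.** The reach of the error is limited. ANYsevere_bin rests on one selected or averaged day 7-10 value, so it cannot serve as the sustained six-week co-primary, which is correctly defined with 110. The in-person recording outcome, the mean blood pressure co-primaries and the power figures do not depend on it either. Table 3 has no row for it, and no analysis in the ANALYTIC APPROACH names it. All of that stands.

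The intended value is also plain from the row's own description and its two components, so a careful programmer might catch the slip. That makes harm less likely but does not remove it: the derivation column is the one a programmer follows, and a wrong 0/1 value passes any range check.

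The percentages rest on a model. The power section gives no time point for the means and SDs, and its wording could be read as confining them to women with severe hypertension, although Table 6 treats them as general baselines. The absolute rates are therefore illustrative. The ratio is sturdier, staying between 2.8 and 3.2 at baseline means across the whole range of correlations.

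Finally, the bias between arms arises only if the tight arm really has fewer diastolic readings of 90 or more at days 7-10, which is something the trial is testing. It is a possible bias, not a certain one.

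**Conclusion.** The concern holds. The contradiction is certain from the text, and following the printed derivation gives a wrong variable. The estimated size is about 30% to 32% of women coded severe instead of 10.3% to 10.6%, given normality, the protocol's means and SDs applied at days 7-10, and a correlation of 0.5 to 0.7. Over correlations from 0 to 0.9, roughly 64% to 68% of flagged women would be false positives and 79% to 99% would have diastolic pressure of 90 or more. The variable would then mostly reflect the tight-arm diastolic goal. The damage is confined to this day 7-10 outcome, but it must be corrected before the variable is analysed.

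**What to change.** Change the ANYsevere_bin derivation to SBP710 ≥ 160 OR DBP710 ≥ 110. Equivalently, set it to 1 when SBPsevere710_bin = 1 or DBPsevere710_bin = 1, which ties it to its components. This restores the plan's own definition of an analysis variable and changes no treatment rule. Check any program already written from the table, and add a consistency check that no woman is 1 on ANYsevere_bin and 0 on both components. The cost is one line in the table and one in the code; no new data are needed and the sample size is unchanged.
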